1 INSTITUTIONAL STATEMENT OF COMPLIANCE

Each institution engaged in this research will hold a current Federal Wide Assurance (FWA) issued by the Office of Human Research Protection (OHRP), and/or will be guided by the review and deliberations of an Institutional Review Board (IRB)/Independent or Institutional Ethics Committee (IEC) that must be registered with OHRP as applicable to the research.

The study will be carried out in accordance with the following as applicable:

- United States (US) Code of Federal Regulations (CFR) 45 CFR Part 46: Protection of Human Subjects
- Food and Drug Administration (FDA) Regulations: 21 CFR Part 50 (Protection of Human Subjects), 21 CFR Part 54 (Financial Disclosure by Clinical Investigators), 21 CFR Part 56 (IRBs), 21 CFR Part 11, and 21 CFR 812 (Investigational Device Exemptions)
- The International Council for Harmonization (ICH) of Technical Requirements for Registration of Pharmaceuticals for Human Use (ICH) E6(R2) Good Clinical Practice (GCP), and the Belmont Report: Ethical Principles and Guidelines for the Protection of Human Subjects of Research, Report of the National Commission for the Protection of Human Subjects of Biomedical and Behavioral Research
- Any additional applicable Federal, State, and Local Regulations and Guidance

4 PROTOCOL SUMMARY

4.1 Executive Summary

In December 2019, the Wuhan Municipal Health Committee identified an outbreak of viral pneumonia cases of unknown origin. Severe acute respiratory syndrome coronavirus type 2 (SARS-CoV-2) was shortly thereafter identified as the etiological agent for Coronavirus Disease 2019 (COVID-19). Recent reports demonstrate that viral load strongly correlates with disease severity, progression, and mortality in SARS-CoV-2 infected humans.¹⁻³ A higher number of health risk factors equates to a higher saliva viral load, with saliva viral load being superior to nasopharyngeal viral load as a predictor of mortality.² Indeed, many of the tissues and glands in the oral cavity have been documented to have high levels of ACE2 expression, highlighting the importance of the oral cavity in understanding both disease progression and oral-lung transmission via aspiration.⁴⁻⁵

There are currently no FDA cleared or approved therapies that directly target early (i.e., within 3 days of symptom appearance) mild to moderate COVID-19 without risk factors for progression to severe disease nor are there treatments directed locally to the high SARS-CoV-2 viral loads observed in the upper respiratory tract or oral cavity. Systemically administered antibody therapies and convalescent plasma have recently shown clinical evidence of nasopharyngeal viral load reductions and improved clinical outcomes in non-hospitalized populations.⁶⁻⁸ However, subsequent emergency use authorizations have restricted these therapies only to populations with risk factors for progression to severe disease and hospitalization and all require infusions in a clinical setting. The diversity of genetic variants of concern is increasing and demonstrate enhanced transmissibility and are more resistant to existing antibody therapies and vaccines.⁹⁻¹¹ The extreme magnitude of transmission in India and Brazil will give rise to a plethora of new variants some of which will almost certainly be of significant concern for the effectiveness of antibody therapies and vaccines that depend on neutralizing antibodies to exert their effect. These existing limitations underscore the need for innovative therapeutic countermeasures that can be made widely available in an equitable fashion and directly address the issue of emerging variants.

The Mechanisms of Action (MOA) of RD-X19 are through both direct and indirect antiviral effects. RD-X19 inactivates cell-free SARS-CoV-2 by as much as 99.99% and inhibits cell-associated replication of the virus by 99.9% when measured at 24 hours after a single treatment *in vitro*. Cell-free SARS-CoV-2 is inactivated directly by 425nm visible blue light and indirectly, during and after light therapy through photobiomodulation of human tissue. One of the putative antiviral mechanisms may involve upregulation of nitric oxide (NO) in epithelial cells via RD-X19-induced increased nitric oxide synthases (NOSs) and stimulation of the instantaneous release of the body's bound stores of NO. It is hypothesized that photoimmunomodulation of the respiratory epithelium signals additional effector cells of the innate immune system. The innate immune effectors include natural killer (NK) cells, monocytes, additional macrophages, and dendritic cells (professional antigen presenting cells) that rapidly proliferate and swarm the infecting virus. The innate immune response is our most ancient form of immunity and through pathogen-only protein pattern

recognition attack the pathogen at the site(s) of infection and end-organ pathology. The technology utilized by RD-X19 has been repeatedly demonstrated to provide high-level viral inactivation in multiple, consistent, expert-laboratory *in vitro* studies. The direct cell-free inactivation of virus by visible blue light presents a transformational opportunity for therapy that is not antigen-directed or antigen-specific, unlike adaptive immunity induced or provided by vaccines and monoclonal antibodies.

Herein we report *in vivo* clinical proof of concept from our phase I/II Randomized, Sham-controlled, Double-blind Safety, Tolerability and Bioeffect Study (RCT) - EB-P12-01 (ClinicalTrials.gov Identifier NCT04662671). In summary, a total of 31 study subjects were randomized 2:1 into this RCT evaluating the RD-X19 device vs. Sham control. The protocol was open to individuals diagnosed positive by an FDA-authorized SARS-CoV-2 antigen test performed within 24 hours of enrollment with the presence of two or more COVID-19 signs and symptoms of \geq moderate severity (using guidance applied to severity grading of Treatment Emergent Adverse Events (TEAEs)) with initial symptoms no longer than 3 days prior to study enrollment. The listing of inclusion and exclusion criteria can be found in the ClinicalTrials.gov reference above.

Primary safety analyses returned the following results: no SAEs, no medically attended or device-related TEAEs (all TEAEs captured were the appearance or worsening of COVID-19 related signs or symptoms). All TEAEs were attributed to COVID-19, and, notably, there were no local site reactions including no changes within the oral cavity indicative of pathology reflecting clinically meaningful potential changes to the oral microbiome. The device was completely safe and exceptionally well-tolerated in this study.

Bioeffects (efficacy) included evaluation of reductions in mean \log_{10} salivary viral load from baseline through study day 8 via RT-qPCR and time to sustained clearance of COVID-19 signs and symptoms, defined as all COVID-19 signs or symptoms graded as 0 (absent) or 1(mild) with no reoccurrence of any sign or symptom of severity score >1 after clearance was achieved.

The EmitBio RD-X19 is safe, reduces salivary viral load 100-fold after 4 days of treatment at study day 5 and 1000-fold (99.9%) at study day 8 – a full 72 hours after completion of treatment. This represents a profound reduction in salivary viral load which is highly correlated with clinical improvement of COVID-19. In our study, signs and symptoms of COVID-19 resolved 57 hours faster in the RD-X19 treated group than in the sham control group; a result that is both clinically meaningful and statistically significant. No study volunteer required medical intervention other than self-medication with OTC remedies. There were no study subjects that discontinued participation.

EmitBio will continue efforts to understand the detailed mechanisms of action that inactivate SARS-CoV-2 and inhibit its replication during and after application of RD-X19. This technology presents an unprecedented opportunity for protection that is NOT antigen-directed or antigen-specific, with a high likelihood of mitigating the threat posed by current SARS-CoV-2 variants as

well as novel pre-emergent coronavirus strains. RD-X19 results in inactivation of all variants of SARS-CoV-2 tested to date, including B.1.1.7, B.1.351, and additional variant strains obtained from California and New York. (unpublished results)

4.1.1 Study Goals

This is a randomized, sham controlled, dose finding study of the EmitBio RD-X19 device in individuals with symptomatic COVID-19 in the outpatient setting. Study subjects will self-administer treatment twice daily for 7 days with a one week follow-up period at Day 14 (+/- 2 days) and will not be aware of which treatment group to which they have been randomized. Clinical outcomes will be assessed via patient reported outcomes (disease assessment and diary cards) and virologic outcomes will be assessed post baseline on Days 3, 5, 8, and 14 via biospecimen collection.

The primary goal of the study is to evaluate multiple doses of the RD-X19 treatment device and establish evidence for safety and efficacy for a single selected RD-X19 dose compared to sham in SARS-CoV-2 infected individuals with outpatient COVID-19. The primary efficacy outcomes are: (i) time to sustained symptom resolution in all patients (mild or moderate disease at baseline); and (ii) time to sustained symptom resolution in patients with mild disease at baseline. Other clinical and microbiological outcomes will also be assessed.

Safety and tolerability (local reactogenicity) will be assessed actively and study subject diary card data recorded at each clinic visit by review of potential treatment emergent adverse events (TEAEs) and targeted oral and physical examinations. Volunteers will be instructed to contact designated clinical trial staff for AEs of a medically-urgent nature as soon as is practically possible and to seek immediate medical care, if needed. On study days 2 and 4 between clinic visits, study personnel will contact each subject by phone for additional safety monitoring. Study subjects who experience progression of disease to a grade 3 severity score (e.g $\text{SpO}_2 \leq 93\%$, or respiratory rate $\geq 30/\text{minute}$ on room air) will be instructed to urgently seek medical care at their nearest Urgent Care or Emergency Department. Study subjects who progress to severe acute respiratory distress syndrome with substantial risk for mortality without immediate medical intervention will be referred directly by site staff to their closest hospital. All study subjects who are hospitalized will be tracked to assess time to hospital discharge or death; the time and date of these events will be captured as part of the trial data.

Metabolic, liver, kidney and hematological laboratory evaluations will be performed at baseline and at Day 14 or early termination (and potentially during unscheduled) clinic visits. Methemoglobin assessments will be performed at baseline and Day 14.

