4.3 Study Schedule of Activities

| Study Procedures | Screening, Enrollment & Randomization | Follow-up Period (Visit Window) | | | | | | |
|---|---|------------------------------------|-------------------------------------|-------------------------------------|-------------------------------------|-------------------------------------|-------------------------------------|-------------------------------------|
| | | 1 @ Each Study Day | 2 | 3 | 4 | 5 (-1 to +1) | 8 (-1 to +1) | 14/ET (-2 to +2) |
| Informed Consent | | X | | | | | | |
| COVID-19 Testing - SARS-CoV-2 Rapid Antigen Test* | | X | | | | | X | X |
| Medical History & Physical Examination | | X | | Changes since last visit only | | Changes since last visit only | X | X |
| Oropharyngeal Assessment | | X** | | Changes since last visit only | | Changes since last visit only | X | X |
| Urine Pregnancy Test | | X | | | | | | |
| Concomitant Medication History/New | Baseline | | Changes since last visit only | | Changes since last visit only | Changes since last visit only | Changes since last visit only | Changes since last visit only |
| Blood Draw (CMP, CBC, SARS-CoV-2 antibody) | | X | | | | | | X |
| Methemoglobin | | X | | | | | | X |
| Vital Signs | | X | | X | | X | X | X |
| Adverse Event Assessment / Reactogenicity | Baseline | | X | | X | X | X | X |
| Demographics, Inclusion / Exclusion Review | | X | | | | | | |
| Diary Dispensation (Diary Card Training) / Collection | | X | | | | X | X | X |
| Dispense RD-X19 Device / Treatment at Site*** | | X | | X | | X | | |
| SARS-CoV-2 Biospecimen collection for viral assays (2 specimens – saliva and nasopharyngeal swab)**** | | X | | X | | X | X | X |
| Extra saliva specimen collection for exploratory oral microbiome assessment | | X | | | | | X | X |
| COVID-19 Disease Assessment | | X | | | | | X | X |
| Telephone Call for Safety Monitoring and Compliance | | | X | | X | | | |
| Collect RD-X19 Device | | | | | | | X | |

* Subjects presenting at the time of screening that have tested positive via a SARS-CoV-2 rapid antigen test at or within the past 24 hours of the screening visit and can provide documentation confirming proper identification, the date of the test and testing location, positivity of the result, and name/identity of the assay used to generate the result, are also eligible for enrollment and the rapid antigen test does not have to be repeated at the site.

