8.5 Device Discontinuation

8.5.1 Study Pausing Criteria

If observations of an SAE or patterns of discrete or non-resolving device-related TEAEs grade 2 or higher in the same SOC PT are observed in a single subject, dosing will be discontinued for that subject and observed at regulatory scheduled follow up visits.

EB-P20-01 enrollment in any Cohort will be paused if any of the following events occur:

- Any subject experiences a device related SAE.
- Any subject experiences laryngospasm, bronchospasm or anaphylaxis within 2 hours after treatment.
- Two (2) or more subjects experience an allergic reaction such as generalized urticaria (defined as occurring at three or more body parts) within 72 hours after treatment.
 - Potential photoallergy or phototoxicity to one or more photosensitizing drugs in the subject's medical history should be investigated in all cases.

See “Medications that Increase Sensitivity to Light: A 1990 Listing (Levine 1990).”

- Three (3) or more subjects experience a Grade 2 or higher TEAE (including local, systemic and/or clinical laboratory abnormalities), in the same SOC grouping of Preferred Terms based on the Medical Dictionary for Regulatory Activities (MedDRA) coding, considered to be related to RD-X19.

While the study is paused, attribution will be determined and assigned and the SMC will be notified that a consultation is required. Given the frequency of visits and the duration of the protocol, study device use may continue in unaffected subjects within a cohort until a recommendation is provided to unpause or terminate cohort enrollment by the SMC.

The SMC, when convened by the sponsor, will not only make a recommendation to unpause enrollment or discontinue dosing in a given cohort, but will also make a recommendation to the sponsor for ascending, or descending from Cohort A in the event safety/tolerability signals are observed with the first 24 J/cm² RD-X19 device.

A study volunteer may elect to discontinue participation in the trial at any time. Investigative staff will ask the volunteer to return for an early termination evaluation, but they are under no obligation to do so. All study subjects must return the RD-X19 device at study termination and study staff must verify that the device serial number matches the study subject to whom it was assigned.

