- Subjects will be observed in the clinic for at least 30 minutes post the first RD-X19 illumination. The oropharynx and surrounding tissues will be examined. Reactogenicity assessments will be performed on Day 1 in the clinic on days 3, 5, 8, and 14 by subjects' diary card entries. Interim or unscheduled targeted physical examinations will be performed, if necessary, to evaluate TEAEs.
- Vital signs:
Vital sign measurements will include systolic and diastolic BP, HR, breaths per minute, oral temperature and oxygen saturation via a pulse co-oximeter. Vital signs will be measured at timepoints specified in protocol section 4.3. Subjects must not eat or drink anything hot or cold within 10 minutes prior to taking their oral temperature or using the RD-X19 device. All subjects will be issued thermometers and small pulse oximeters to measure oral temperature and O₂ saturation on a twice daily basis and record the results on their diary card.
- Clinical laboratory evaluations:
 - Fasting is not required before collection of clinical laboratory evaluations.
 - Urine pregnancy test will be performed locally by the site laboratory at the screening visit. Results must be confirmed as negative prior to randomization on Day 1 and allocation and use of the RD-X19 device.
 - Clinical laboratory evaluations CMP and CBC (diff) will be performed locally by the site selected laboratories.
 - Clinical safety laboratory evaluations will be performed locally by the site laboratory.

- Blood will be collected at timepoints specified in the protocol section 4.3.
- Methemoglobin will be measured as stipulated in the study procedures table using the Massimo® non-invasive pulse oximetry device.
- Anti-Spike IgG will be measured at screening/baseline and on Day 14.
- Absolute Neutrophil Count to Absolute Lymphocyte Count Ratio (N/L ratio) and Red cell distribution width (RDW) will both be recorded from the CBC panel.
- Diary Cards:

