10.4.2 Safety Analyses

Summaries will be presented by treatment arm on the Safety Population. Adverse device effects will be coded using the latest version of the Medical Dictionary for Regulatory Activities (MedDRA). Treatment Emergent Adverse Events (TEAE), vital signs, and methemoglobin will be summarized using descriptive statistics. Other safety data including prior and concomitant medications will be listed.

TEAEs are any event not present prior to the initiation of the treatments or any event already present that worsens in either intensity following exposure to the treatments. Number and percent of subjects reporting TEAEs will be tabulated by treatment group. Summaries will be presented by system organ class and preferred term, and further by severity and relationship to study treatment. In the summaries of incidence rates (frequencies and percentages), severity and relationship to treatment, subjects who report more than one event that are mapped to the same preferred term will be counted only once under the strongest severity and relationship, accordingly.

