### 5.6.6 Other Assessments

Following assessment results will be presented in subject data listing: medical history, physical examination, clinical laboratory evaluations, concomitant medications.

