## List of Data Listings

Number	Description
16.2.1	Subject Disposition
16.2.2.1	Protocol Deviations
16.2.2.2	Informed Consent, Eligibility Criteria, and Randomization
16.2.2.3	General Comments
16.2.4.1	Demographics
16.2.4.2	Medical/Surgical History
16.2.4.3	COVID-19 Symptom Assessment at Visit 1/Day 1
16.2.5.1	Subject Dosing Diary, Study Device Dispensing at Visit 1/Day 1, and Illumination Treatment at Site
16.2.5.2	Subject Dosing Diary and Study Device Collection
16.2.5.3	Treatment Record at End of Study
16.2.5.4	Treatment Application Log
16.2.6.1	COVID-19 Symptom Assessment and Severity Score from Subject Diary
16.2.6.2	Viral Load via Saliva and Nasopharyngeal Swab Collection
16.2.6.3	Derived Primary and Secondary Clinical Outcomes
16.2.7	Adverse Events
16.2.8.1	Biospecimen Lab Collection
16.2.8.2	Pregnancy Test (Female Subjects Only)
16.2.9.1	SARS-CoV-2 Rapid Antigen Test and Methemoglobin Measurement
16.2.9.2	COVID-19 Disease Assessment
16.2.9.3	Reactogenicity Assessment and Medical Encounter/Hospitalization
16.2.9.4	Oropharyngeal Assessment
16.2.9.5	Vital Signs
16.2.9.6	Physical Examination
16.2.9.7	Prior and Concomitant Medications
16.2.9.8.1	Medical Encounter Questionnaire (Part 1)
16.2.9.8.2	Medical Encounter Questionnaire (Part 2)
16.2.9.8.3	Medical Encounter Questionnaire (Part 3)

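### The SAP plans no by-arm summary of the Day 14 chemistry and blood-count values; only abnormalities that an investigator judges clinically significant are compared with sham, as adverse events.

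*Protocol*

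**What the plan says.** **Collection.** Protocol 4.1.1 states that "Metabolic, liver, kidney and hematological laboratory evaluations will be performed at baseline and at Day 14 or early termination". In the schedule (Protocol 4.3) the row beginning "Blood Draw (CMP, CBC, SARS-CoV-2 antibody" is marked at Day 1 and at Day 14/ET. Protocol 9.2 adds, under clinical laboratory evaluations, that "Anti-Spike IgG will be measured at screening/baseline and on Day 14".

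**Analysis.** Protocol 10.4.2 names what is summarised: "Treatment Emergent Adverse Events (TEAE), vital signs, and methemoglobin will be summarized using descriptive statistics". The rest is covered by "Other safety data including prior and concomitant medications will be listed". SAP 5.6.6 follows this: "Following assessment results will be presented in subject data listing: medical history, physical examination, clinical laboratory evaluations, concomitant medications". SAP 5.6.4 and 5.6.5 give vital signs and methemoglobin actual values and change from baseline by treatment group.

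**Other uses of laboratory findings.** Protocol 9.1.2 turns clinically significant findings after first device use into TEAEs, and the TEAE definition in 9.2.1 expressly covers abnormal laboratory findings. The pausing rule in 8.5.1 counts related Grade 2 or higher TEAEs, "including local, systemic and/or clinical laboratory abnormalities".

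**The concern.** The primary goal in Protocol 4.1.1 includes evidence of safety for a selected dose compared to sham. Liver, kidney, metabolic and blood-count values are objective measures taken from everyone before treatment and at the end of follow-up. In a population where everyone has COVID-19, a changed value in one subject is hard to read, because disease and device are both candidate causes. The sham arm is there to resolve that.

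A by-subject listing does not make the comparison, and the adverse event tables make it only for values that someone has called clinically significant. A modest but systematic change in, say, a liver enzyme or the lymphocyte count could go unseen if no single value crossed that line. The doses add to the interest: Protocol 6.5.1 puts the Cohort A energy per dose 50% above that of the previous study, and the Cohort B daily dose up to 100% above it, so earlier laboratory reassurance does not simply carry over.

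**Working it through.** The documents give no figure for laboratory data, so there is none to reproduce. The check is a trace of the outputs, followed by an illustration of what a by-arm summary would deliver.

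**1. Trace of planned outputs (SAP 7.2)**

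| Data | By-arm table | Listing |
|---|---|---|
| TEAEs | 14.3.1.1 to 14.3.1.4 | 16.2.7 |
| Reactogenicity | 14.3.2 | 16.2.9.3 |
| Oropharyngeal assessment | 14.3.3 | 16.2.9.4 |
| Vital signs | 14.3.4.1 to 14.3.4.6, with change | 16.2.9.5 |
| Methemoglobin | 14.3.5, with change | 16.2.9.1 |
| CMP, CBC | none | none |
| Anti-Spike IgG, Day 14 | none | none |

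The closest listing title, 16.2.8.1 "Biospecimen Lab Collection", records whether saliva and nasopharyngeal samples were obtained. It holds no blood result. Listing 16.2.8.2 is the pregnancy test, and 16.2.9.1 is the rapid antigen test and methemoglobin. So the laboratory listing promised in SAP 5.6.6 appears neither in the index nor among the shells.

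Two consequences follow:
- Protocol 9.1.1 flags a neutrophil-to-lymphocyte ratio of 4.5 or more and a red cell distribution width of 15 or more as possible risk factors for progression. Protocol 9.2 requires both to be recorded. No planned output shows them.
- Baseline serostatus defines the mFAS and appears in Table 14.1.3. The index sources that table to Listings 16.2.4.1 (demographics) and 16.2.9.5 (vital signs), and neither shell has an antibody column.

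**2. The one indirect route to a by-arm result**

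Protocol 9.1.2 and 9.2.1 make clinically significant laboratory findings TEAEs. Section 9.2.1 also requires all TEAEs to be documented whatever their relationship to the device. SAP 5.6.1 tabulates them by treatment, and SAP 5.6 supplies a pooled sham column. This is a genuine by-arm comparison, but of counts that pass a judgement threshold.

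**3. Precision of a by-arm summary of change (illustration)**

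Inputs: the Final Cohort is up to 180 (SAP 3.3) at 2:1, so 120 RD-X19 and 60 sham. A dose-finding cohort is 20:10. Assume both draws are available for everyone.

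SE of a difference in mean change = SD × √(1/n₁ + 1/n₂); 95% half-width = 1.96 × SE.

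- 120:60: √(1/120 + 1/60) = 0.158; × 1.96 = **0.31 SD**
- 100:50: 0.173; × 1.96 = 0.34 SD
- 96:48 (applying to 120:60 the 20% dropout that SAP 3.3 assumes for the mFAS): 0.177; × 1.96 = 0.35 SD
- 20:10: 0.387; × 1.96 = 0.76 SD

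With the SAP's pooled sham column (60 + 10 = 70), the Final Cohort dose at 120:70 gives 0.150 × 1.96 = 0.29 SD. The Cohort A dose at 20:70 gives 0.254 × 1.96 = 0.50 SD.

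**4. How coarse the adverse event route is (illustration)**

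Two-sided 5% comparison of two proportions at 120:60, pooled variance under the null and unpooled under the alternative. The sham rates are assumed, since the documents give none. Example: sham 5%, active 20%.

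- Pooled rate = (60 × 0.05 + 120 × 0.20)/180 = 0.15
- SE under the null = √(0.15 × 0.85 × 0.025) = 0.0565
- SE under the alternative = √(0.05 × 0.95/60 + 0.20 × 0.80/120) = 0.0461
- Power = Φ[(0.15 − 1.96 × 0.0565)/0.0461] ≈ 0.80

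The same calculation at sham rates of 2% and 10% needs about 15% and 28% on active for 80% power. Even pooled over all laboratory terms, counts of flagged abnormalities would reveal only large differences.

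**The case against.** The plan is deliberate and self-consistent. Protocol 10.4.2 and SAP 5.6.6 agree on listing only, so there is no conflict between the documents. The safety outcomes in Protocol 6.4 are SAEs, TEAEs and application-site reactions; CMP and CBC are not named as outcome measures. Light is applied locally, and vital signs and methemoglobin, also objective, are tabulated by arm. SAP section 6 calls the outputs examples that may be modified. All of this stands, and it limits the weight of the point. It does not explain why two sets of objective safety values get change tables while the CMP and CBC, drawn on the same two occasions as methemoglobin, do not.

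Three stronger readings are tempting, and the documents do not support them.

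- *The Day 14 bloods feed no by-arm result at all.* They do, through the TEAE tables. Because TEAEs are counted regardless of attribution, that comparison does not depend on anyone separating device from disease in a single subject.
- *The trial cannot separate a device effect on these values from COVID-19.* Randomisation and paired draws make the comparison possible. What is missing is a planned display.
- *Leaving Day 14 anti-Spike IgG unanalysed fails a stated objective.* Only the baseline antibody result is used (mFAS, Cox covariate, baseline table), but antibody response is not a primary, secondary or exploratory endpoint in either document.

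**Conclusion.** The point holds as a descriptive reporting gap. There are no by-arm tables of CMP or CBC values and no listing shells for them, although SAP 5.6.6 promises a listing. What is lost is by-arm sight of mean shifts and of changes that no investigator calls clinically significant.

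The size of what is forgone depends on enrolment. A fully expanded Final Cohort with complete draws would place a difference in mean change within about ±0.31 SD, or about ±0.35 SD with 20% missing. A single 20:10 cohort would give only about ±0.76 SD, so there the table would be little more than a safety display. These figures assume a normal approximation and equal SDs in the two arms.

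The reading that only clinically significant values reach the TEAE tables rests on Protocol 9.1.2. The definition in 9.2.1 is broad enough to let an investigator record more, but nothing requires it. Primary endpoints, error rates and the pausing rule are untouched. Severity is low to moderate.

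**What to change.** In SAP 5.6.6 and 7.2:

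1. Add a descriptive table of CMP and CBC parameters: baseline, Day 14/ET and change from baseline. Include the neutrophil-to-lymphocyte ratio and red cell distribution width, since the protocol already records them.
2. Add a shift table, baseline to Day 14/ET, by laboratory normal range. Use the Appendix 2 grade only where that appendix grades the parameter; its content is not in the text reviewed.
3. Use the safety columns already set in SAP 5.6: each RD-X19 dose, pooled RD-X19 and pooled sham.
4. Add the missing laboratory listing, with antibody results, and cite it as a source for Table 14.1.3.
5. Optional: a descriptive Day 14 anti-Spike IgG summary by arm and baseline serostatus.

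If the sponsor prefers to keep listing only, SAP 5.6.6 should say why that is sufficient, and the listing is still needed.

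The cost is SAP wording, two or three tables and a listing, with no new procedure or sample. The downside is that some differences will appear by chance across many parameters, so the tables should carry no hypothesis tests and be labelled descriptive.
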